7.1.5.3.2. Sponsor Responsibility

If a serious unexpected adverse event is believed to be related to the study drug or study procedures, the sponsor will take appropriate steps to notify all investigators participating in sponsored clinical studies of TEV-48125 and the appropriate regulatory authorities (and IEC/IRB, if appropriate).

In addition to notifying the investigators and regulatory authorities (and IEC/IRB, if appropriate), other measures may be required, including the following:

- altering existing research by modifying the protocol
- discontinuing or suspending the study
- altering the process of informed consent by modifying the existing consent form and informing current study participants of new findings
- modifying listings of expected toxicities to include adverse events newly identified as related to TEV-48125

7.1.6. Protocol-Defined Adverse Events of Special Interest

The following are considered protocol-defined adverse events to be sent to the sponsor's Global Patient Safety and Pharmacovigilance Department for evaluation: ophthalmic adverse events of at least moderate severity, events of possible drug-induced liver injury (AST or ALT $\geq 3 \times$ the

ULN, total bilirubin $\geq 2 \times$ the ULN or INR >1.5), Hy's Law events, or events of suspected anaphylaxis and severe hypersensitivity reactions. Severe hypersensitivity reactions will be monitored using the diagnostic criteria for anaphylaxis as outlined by the 2006 Joint National Institute of Allergy and Infectious Disease/Food Allergy and Anaphylaxis Network Second Symposium on Anaphylaxis (Sampson et al, 2006 [also see Appendix F]). In the event of suspected anaphylaxis, vital signs, including oxygen saturation and respiration rate, will be measured. Other assessments will be performed at the discretion of the investigator.

The process for reporting a protocol-defined adverse event is the same as that for reporting a serious adverse event (see Section 7.1.5.3). Protocol-defined adverse events for reporting to Pharmacovigilance Department can be either serious or nonserious according to the criteria outlined in Section 7.1.5.1.

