7.1. Adverse Events

7.1.1. Definition of an Adverse Event

An adverse event is any untoward medical occurrence in a patient administered a pharmaceutical product, regardless of whether it has a causal relationship with this treatment.

In this study, any adverse event occurring after the clinical study patient has signed the informed consent form for this study should be recorded and reported as an adverse event.

An adverse event can, therefore, be any unfavorable and unintended physical sign, symptom, or laboratory parameter that develops or worsens in severity during the course of this study, or significant worsening of the disease under study or of any concurrent disease, whether or not considered related to the study drug. A new condition or the worsening of a pre-existing condition will be considered an adverse event. Stable chronic conditions (such as arthritis) that are present before study entry and do not worsen during this study will not be considered adverse events.

Accordingly, an adverse event can include any of the following:

- intercurrent illnesses
- physical injuries
- events possibly related to concomitant medication
- significant worsening (change in nature, severity, or frequency) of the disease under study or other pre-existing conditions (Note: A condition recorded as pre-existing that is intermittently symptomatic [eg, headache] and that occurs during this study should be recorded as an adverse event.)
- drug interactions
- events occurring during diagnostic procedures or during any follow-up period of this study
- laboratory or diagnostic test abnormalities that result in the withdrawal of the patient from the study, are associated with clinical signs and symptoms or a serious adverse event, or require medical treatment or further diagnostic work-up, or are considered by the investigator to be clinically significant (Note: Abnormal laboratory test results at the screening visit that preclude a patient from entering the study or receiving study drug are not considered adverse events.)
- all events of possible drug-induced liver injury with hyperbilirubinemia (defined as AST or ALT $\geq 3 \times$ the ULN, plus either total bilirubin $\geq 2 \times$ the ULN or INR > 1.5) or

Hy's Law events require immediate study treatment cessation and reporting as a serious adverse event. Refer to [Appendix E](#) for guidance regarding monitoring patients with elevated liver function tests.

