7.3. Adverse Events

All adverse events will be coded using the MedDRA version 18.1.

For adverse event recording, the study period is defined for each patient as the time period from signature of the informed consent form for this study through the follow-up visit (approximately 7.5 months after the final dose of study drug). Adverse events will be collected at each visit via adverse event inquiry. The onset and end dates, duration (in case of adverse event duration of less than 24 hours), action taken regarding study drug, treatment administered, and outcome for each adverse event must be recorded on the source documentation and transcribed onto the CRF.

The following are considered protocol-defined adverse events to be sent to the sponsor's Global Patient Safety and Pharmacovigilance Department for evaluation: ophthalmic adverse events of at least moderate severity, events of possible drug-induced liver injury (aspartate aminotransferase or alanine aminotransferase $\geq 3 \times$ the upper limit of the normal range [ULN], total bilirubin $\geq 2 \times$ the ULN or international normalized ratio >1.5), Hy's Law events, or events of suspected anaphylaxis and severe hypersensitivity reactions. Severe hypersensitivity reactions will be monitored using the diagnostic criteria for anaphylaxis as outlined by the 2006 Joint National Institute of Allergy and Infectious Disease/Food Allergy and Anaphylaxis Network Second Symposium on Anaphylaxis ([Sampson et al 2006](#)). In the event of suspected anaphylaxis, vital signs, including oxygen saturation and respiration rate, will be measured.

Summaries by treatment group and overall will be presented for treatment-emergent adverse events (overall and by severity), treatment-emergent adverse events determined by the investigator to be treatment-related adverse events (overall and by severity), serious adverse events, protocol-defined adverse events, adverse events causing discontinuation from the study, non-serious treatment-emergent adverse events, and prior to treatment adverse events. Additionally the injection site reactions recorded as adverse events will be summarized by treatment group separately.

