ALP	$\geq 3 \times \text{ULN}$
GGT	$\geq 3 \times \text{ULN}$
Lactate dehydrogenase	$\geq 3 \times \text{ULN}$
Blood urea nitrogen	$\geq 10.71 \text{ mmol/L}$
Creatinine	$\geq 177 \mu\text{mol/L}$
Uric acid Men	$\geq 625 \mu\text{mol/L}$
Women	$\geq 506 \mu\text{mol/L}$
Bilirubin (total)	$\geq 34.2 \mu\text{mol/L}$
Hematology	
Hematocrit Men	$< 0.37 \text{ L/L}$
Women	$< 0.32 \text{ L/L}$
Hemoglobin Men	$\leq 115 \text{ g/L}$
Women	$\leq 95 \text{ g/L}$
WBC counts	$\leq 3 \times 10^9/\text{L}$ or $\geq 20 \times 10^9/\text{L}$
Eosinophils	$\geq 10\%$
Absolute neutrophil counts	$\leq 1 \times 10^9/\text{L}$
Platelet counts	$\leq 75 \times 10^9/\text{L}$ or $\geq 700 \times 10^9/\text{L}$
Urinalysis	
Blood (HGB)	≥ 2 unit increase from baseline
Glucose	≥ 2 unit increase from baseline
Ketones	≥ 2 unit increase from baseline
Total protein	≥ 2 unit increase from baseline

ALP=alkaline phosphatase; ALT=alanine aminotransferase; AST=aspartate aminotransferase; GGT=gamma-glutamyl transpeptidase; HGB=hemoglobin; INR=international normalized ratio; ULN=upper limit of normal range; WBC=white blood cell

Serum beta-human chorionic gonadotropin (β -HCG) tests will be performed for all women of childbearing potential at screening (visit 1), and urine β -HCG tests will be performed for women of childbearing potential at visits 2 through 5. Positive pregnancy test results will be listed.

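### The protocol-defined liver event is a series of single values in protocol 7.1.6 and SAP 7.3 but a combination in protocol 7.1.1 and Appendix E, and no planned output counts the combined signal independently of site reporting

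*Protocol*

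**What the plan says.** Protocol 7.1.6 lists the events that sites must send to the sponsor's pharmacovigilance department. The liver item opens with "events of possible drug-induced liver injury (AST or ALT" at or above 3 times ULN, goes on to total bilirubin at or above 2 times ULN, and closes with "the ULN or INR >1.5), Hy's Law events, or events of suspected anaphylaxis". Hy's Law cases are thus a separate item. The same section says that protocol-defined events "can be either serious or nonserious according to the criteria outlined in Section 7.1.5.1".

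SAP 7.3 carries the item over unchanged: "events of possible drug-induced liver injury (aspartate aminotransferase or alanine aminotransferase" and the rest of the series, again without a joining word. It then plans a summary of protocol-defined adverse events by treatment group and overall, and a listing of them.

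Protocol 7.1.1 covers "all events of possible drug-induced liver injury with hyperbilirubinemia (defined as AST or ALT" at or above 3 times ULN, "plus either total bilirubin" at or above 2 times ULN or INR above 1.5. It attaches a consequence: these and Hy's "Law events require immediate study treatment cessation and reporting as a serious adverse event".

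The stopping rules in protocol Appendix E also combine an enzyme rise with bilirubin or INR, but with bilirubin strictly above 2 times ULN and INR above 1.5 times its ULN. SAP 7.6, Table 7, sets single-test criteria for ALT, AST and total bilirubin, among others.

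**The concern.** Safety is the primary objective, and protocol 1.4.1.1 names liver enzyme elevation as a potential risk. The liver item in 7.1.6 can be read in two main ways. Literally, any one of the three values qualifies. Read with 7.1.1 and Appendix E in mind, it looks like a combination with the joining words left out. Neither protocol nor SAP says which is meant.

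The SAP gives no rule for deriving the item from laboratory data, so its content comes from what about 140 centers choose to report. The liver entries in the protocol-defined event summary could then be isolated laboratory changes at one center and combined events at another. A reader who wants to know how many patients had an enzyme rise together with raised bilirubin or INR would find no planned output that gives the number independently of site reporting.

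**Working it through.** The plan states no figure on this point, so there is none to reproduce. The check is a comparison of the texts, a count of patterns, and a look at what the planned outputs can show.

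**1. The four places side by side**

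| Place | Enzyme | Link | Bilirubin | INR | Purpose |
|---|---|---|---|---|---|
| Protocol 7.1.6 | ≥3× ULN | comma, then or | ≥2× ULN | >1.5 | notification; serious or nonserious |
| SAP 7.3 | ≥3× ULN | comma, then or | ≥2× ULN | >1.5 | summary and listing |
| Protocol 7.1.1 | ≥3× ULN | plus either | ≥2× ULN | >1.5 | serious event report; treatment cessation |
| Appendix E | ≥3× ULN | combined with | >2× ULN | >1.5× ULN | stopping rule |

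**2. Which patterns each reading counts**

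Let A be AST or ALT ≥3× ULN, B be total bilirubin ≥2× ULN, and C be INR >1.5.

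- Series (literal 7.1.6 and SAP 7.3): A or B or C.
- Combination (7.1.1): A and (B or C).

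| Pattern | Series | Combination |
|---|---|---|
| A only | yes | no |
| B only | yes | no |
| C only | yes | no |
| B and C | yes | no |
| A and B | yes | yes |
| A and C | yes | yes |
| A, B and C | yes | yes |

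The series counts 7 of 7 patterns and the combination 3 of 7, so 7 − 3 = 4 change status. Every pattern in the combination is also in the series. Hence

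series count − combination count = n(A only) + n(B only) + n(C only) + n(B and C without A) ≥ 0.

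The documents give none of these four counts or their rates, so the difference cannot be put in patients.

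**3. How this reaches the output**

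SAP 7.3 summarizes and lists protocol-defined adverse events as reported. It specifies no separate liver row and no laboratory-derived rule. The affected quantity is therefore the liver part of that summary and listing.

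**4. What SAP Table 7 adds**

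- A: ALT ≥3× ULN and AST ≥3× ULN, each on all postbaseline values. These counts do not depend on site reporting.
- B: total bilirubin at a fixed 34.2 µmol/L. This equals 2× ULN only if the ULN is 34.2 / 2 = 17.1 µmol/L; the documents do not state the ULN.
- C: no criterion. SAP 7.6 summarizes coagulation tests by visit and as shifts, but flags no INR threshold.
- A and (B or C): no criterion.

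Separate counts n(A) and n(B) do not give n(A and B), which can lie anywhere from 0 (when n(A) + n(B) does not exceed the number of patients) to the smaller of the two. The listing of flagged patients would let a reader match enzymes with bilirubin by hand, but not with INR.

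**The case against.** The strongest reply is that the sections do different jobs. Protocol 7.1.1 is narrower by its own label (it concerns cases with hyperbilirubinemia) and governs serious event reporting and treatment cessation. Protocol 7.1.6 governs notification, admits nonserious events and lists Hy's Law separately. A broad notification tier containing a narrower serious tier makes sense, and SAP 7.3 agrees word for word in substance with 7.1.6. This stands as a coherent reading, so a reader should not infer that the sections necessarily contradict each other. It does not settle the matter, because neither document states that the tiers are nested, and omitted joining words remain plausible given 7.1.1 and Appendix E.

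Three stronger inferences are tempting, and the documents do not support them.

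- **That a dedicated table of liver injury is compromised.** No such table or row is planned.
- **That the safety data cannot be pooled.** The single-test counts in Table 7 are independent of site reporting, the laboratory values are held for both categories, and no inferential analysis is planned. No differential effect by treatment group is shown.
- **That a given number of patients would be misclassified.** No event rate is stated. Protocol 1.3.2 reports no liver function changes in Phase 1 and no laboratory safety signals in Phase 2b, and new patients with confirmed enzymes above 1.5 times ULN are excluded at screening.

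It is also fair to say that the fixed bilirubin criterion in Table 7 is not shown to be wrong, since its relation to the laboratory's ULN is not given.

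**Conclusion.** The point holds as a gap in definition with a limited consequence. The liver part of the protocol-defined adverse event summary and listing depends on how sites read protocol 7.1.6, and no planned output gives a site-independent count of the combined enzyme-plus-bilirubin or INR signal.

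The direction is certain: at the thresholds shared by 7.1.1 and 7.1.6, the combination is a subset of the series, so the literal reading can only give an equal or larger count. The size is unknown and could be small. The conclusion assumes that the liver entries are taken from site reports, as SAP 7.3 implies by giving no derivation rule. The central laboratory data and the single-test counts limit the harm. The change is still worth making, because it costs little and bears on a named potential risk in a study whose primary objective is safety.

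**What to change.** 1. Reconcile protocol 7.1.1, 7.1.6 and Appendix E with SAP 7.3, either to one definition or by stating expressly how the notification, serious-event and stopping tiers relate. The differing bilirubin and INR cut-offs in Appendix E belong in the same check. The sponsor decides which reading is intended; no clinical threshold or stopping rule is proposed here.
2. In SAP 7.6, add derived rows by treatment group for isolated elevations (enzyme, bilirubin and INR each alone) and for the combined enzyme-plus-bilirubin or INR criterion, at the protocol's own reconciled thresholds.
3. Base these rows on the central laboratory data plus any local values recorded in the CRF. Local values matter because Appendix E sends follow-up INR to local laboratories.
4. State how close in time two values must be to count as combined, since none of the four places says.

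The cost is wording in two documents and one derived table. No new data collection is needed.

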7.1.7. Withdrawal Due to an Adverse Event

Any patient who experiences an adverse event may be withdrawn from the study or from study drug at any time at the discretion of the investigator. If a patient is withdrawn because of an adverse event, both the adverse events page and termination page of the CRF will be completed at that time.

The patient will be monitored at the discretion of the investigator (eg, until the event has resolved or stabilized, until the patient is referred to the care of a health care professional, or until a determination of a cause unrelated to the study drug or study procedure is made). The investigator must inform the clinical project physician/clinical leader as soon as possible of all patients who are being considered for withdrawal due to adverse events. Additional reports must be provided when requested.

If a patient is withdrawn from the study or study drug for multiple reasons that include adverse events, the termination page of the CRF should indicate that the withdrawal was related to an adverse event. An exception to this requirement will be the occurrence of an adverse event that, in the opinion of the investigator, is not severe enough to warrant discontinuation but that requires the use of a prohibited medication, thereby requiring discontinuation of the patient. In such a case, the reason for discontinuation would be need to take a prohibited medication, not the adverse event.

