1.4.1.1. Risks of TEV-48125

Identified risks (adverse drug reactions) of TEV-48125 include injection site erythema, administration site pain, injection site pain, injection site pruritus, injection site dermatitis, infusion-related reaction, and drug hypersensitivity. None of the identified risks are considered important risks.

Potential risks for TEV-48125 are perivascular inflammation; development of antidrug antibodies (ADAs); liver enzyme elevations; and cardiovascular consequences of CGRP inhibition, including effects on blood pressure, heart rate, or other cardiovascular parameters.

As described in Section 1.3.2.2, sc TEV-48125 has generally been well tolerated over the ranges of doses evaluated (single doses of 0.02 to 2000 mg in healthy volunteers, multiple doses of 30 to 300 mg in healthy volunteers, and multiple doses of 225 to 900 mg in migraine patients). The most common treatment-emergent adverse events across the clinical program were mild to moderate transient general administration site disorders/reactions. Other commonly reported treatment-emergent adverse events were headache, back pain, and upper respiratory tract infection.

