9.7.2. Safety and Tolerability Analysis

All adverse events will be coded using the Medical Dictionary for Regulatory Activities. Each patient will be counted only once in each preferred term or system organ class category for the analyses of safety. Summaries will be presented for all adverse events (overall and by severity), adverse events determined by the investigator to be related to study treatment (ie, reasonable possibility; see [Section 7.1.4](#)) (defined as related or with missing relationship) (overall and by severity), serious adverse events, and adverse events causing withdrawal from the study. Patient listings of serious adverse events and adverse events leading to withdrawal will be presented.

Injection site erythema, induration, ecchymosis, and pain will be assessed, and severity will be graded as described in [Section 7.9](#), and findings will be listed and summarized.

Changes in laboratory and vital signs measurement data will be summarized descriptively. All values will be compared with prespecified boundaries to identify potentially clinically significant changes or values, and such values will be listed.

The use of concomitant medications will be summarized by therapeutic class using descriptive statistics. Concomitant medications will include all medications taken while the patient is treated with study drug.

Safety data will be summarized descriptively overall, by diagnosis, and by treatment group. For continuous variables, descriptive statistics (n, mean, SD, median, minimum, and maximum) will be provided for actual values and changes from baseline to each time point. For categorical variables, patient counts and percentages will be provided. Descriptive summaries of serious adverse events, patient withdrawals due to adverse events, and potentially clinically significant abnormal values (clinical laboratory or vital signs) based on predefined criteria will also be provided.

If any patient dies during the study, a listing of deaths will be provided and all relevant information will be discussed in the patient narrative included in the clinical study report.

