11.1.2. Protocol Violations

Any deviation from the protocol that affects, to a significant degree, (a) the safety, physical, or mental integrity of the subjects of the study and/or (b) the scientific value of the study will be considered a protocol violation. Protocol violations may include nonadherence on the part of the patient, the investigator, or the sponsor to protocol-specific inclusion and exclusion criteria, primary objective variable criteria, or GCP guidelines; noncompliance to study drug administration; and use of prohibited medications. Protocol violations will be identified and recorded by investigational center personnel in the CRF. All protocol violations will be reported to the responsible IEC/IRB, as required.

When a protocol violation is reported, the sponsor will determine whether to discontinue the patient from the study or permit the patient to continue in the study, with documented approval from the medical expert. The decision will be based on ensuring the safety of the patient and preserving the integrity of the study.

Changes in the inclusion and exclusion criteria of the protocol are **not** prospectively granted by the sponsor. If investigational center personnel learn that a patient who did not meet protocol inclusion and exclusion criteria was entered in a study, they must immediately inform the sponsor of the protocol violation. If such patient has already completed the study or has withdrawn early, no action will be taken but the violation will be recorded.

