APPENDIX B. DISALLOWED MEDICATIONS FOR THE DURATION OF THE STUDY

Patients not using preventive medications for migraine at baseline will be asked not to initiate preventive medications/treatments de novo during the safety extension study. Preventive migraine medications disallowed for these patients for the duration of the study specifically include the following:

- beta-blockers: atenolol, propranolol, metoprolol, nadolol, and timolol
- calcium channel blocker/benzocycloheptene: flunarizine and pizotifen
- antidepressants: amitriptyline, venlafaxine, nortriptyline, and duloxetine
- anti-epileptic medications: topiramate, valproate, carbamazepine, and divalproate
- angiotensin receptor blocker: candesartan and lisinopril
- onabotulinumtoxinA: botox
- triptans/ergots: used as preventive therapies for migraine
- NSAIDs: used as preventive therapy for migraine or on a daily basis for other indications
- devices for migraine prophylaxis
- nerve blocks in the head and neck

Any of the listed medications are allowed if given as topical or eye drops.

Other medications in the same classes but not included in this list are allowed.

**APPENDIX C. NATIONAL INSTITUTES OF HEALTH PATIENT
EDUCATION GUIDELINES OF JUNE 2012**

[figure not shown]
Patient Education

Clinical Center
NATIONAL INSTITUTES OF HEALTH

Giving a subcutaneous injection

What is a subcutaneous injection?

A subcutaneous injection is given in the fatty layer of tissue just under the skin.

A subcutaneous injection into the fatty layer of tissue (pinched up to give the injection) under the skin.

Why are subcutaneous injections given?

These injections are given because there is little blood flow to fatty tissue, and the injected medication is generally absorbed more slowly, sometimes over 24 hours. Some medications that can be injected subcutaneously are growth hormone, insulin, epinephrine, and other substances.

Preparing to give medication

Subcutaneous injections are not given if the skin is burned, hardened, inflamed, swollen, or damaged by a previous injection.

1. Wash your hands thoroughly. This is the best way to prevent infection.
2. Assemble your equipment:

Medication

- May be a multidose vial of liquid or may be a vial with powder that requires “reconstitution.” Follow the manufacturer’s instructions as to what and how much diluent to use. The diluent is usually saline (a mixture of salt water) or sterile water.

Syringe or pen and needle

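### Protocol 7.1.7 takes one group of adverse-event-triggered withdrawals out of the adverse-event reason, and no planned count brings them back

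*Protocol*

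**What the plan says.** Protocol 7.1.7 sets a default for withdrawals, from the study or from study drug, that have more than one reason. If an adverse event is among the reasons, "the termination page of the CRF should indicate that the withdrawal was related to an adverse event". One exception follows. It covers an event that, "in the opinion of the investigator, is not severe enough to warrant discontinuation but that requires the use of a prohibited medication", where use of that medicine then forces the patient to stop. The instruction for this group is: "In such a case, the reason for discontinuation would be need to take a prohibited medication, not the adverse event".

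Withdrawals linked to adverse events are a planned result. Protocol 9.7.2 promises "Descriptive summaries of serious adverse events, patient withdrawals due to adverse events, and potentially clinically significant abnormal values", with patient listings. SAP 7.3 plans a summary of "adverse events causing discontinuation from the study" and a matching listing. Separately, Protocol 9.4.1 and SAP 5.2 tabulate patients who leave by the reason for withdrawal.

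On what happens after a prohibited medicine is used, Protocol 11.1.2 classes such use as a possible protocol violation and says that "the sponsor will determine whether to discontinue the patient from the study or permit the patient to continue in the study". Protocol 7.1.9 also allows individual departures from the protocol when an adverse event occurs, with the investigator and sponsor deciding on continuation.

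**The concern.** In the excepted group the chain begins with an adverse event: no event, no prohibited medicine, no withdrawal. The default rule would record the event as a reason. The exception replaces it, on the investigator's opinion of whether the event alone justified stopping. The effect is one-directional. A withdrawal can move out of the adverse-event category under this rule, but none can move in.

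This matters more here than in many trials. Long-term safety and tolerability is the only primary objective (Protocol 2.2.1). Protocol 3.9 calls the study uncontrolled, there is no placebo arm, and Protocol 9.6 rules out inferential analysis. The share of patients who leave because of adverse events will therefore be read as an absolute figure, with no control arm affected by the same coding.

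**Working it through.** The plan gives no figure for adverse-event withdrawals or for withdrawals due to prohibited medicines, so there is nothing to reproduce. The check is mainly a tracing of the text.

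1. **Disposition (Protocol 9.4.1, SAP 5.2).** This table is by reason for withdrawal. Under 7.1.7 an excepted case carries the prohibited medicine as its reason, so it leaves the adverse-event row. It would be counted under another reason, mixed with any patients who took a prohibited medicine for causes unrelated to an adverse event.

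2. **Summary and listing of adverse events causing discontinuation (Protocol 9.7.2, SAP 7.3).** Two sources are possible.
   - *Termination page.* Excepted cases drop out of both the summary and the listing.
   - *Adverse-event page.* Protocol 7.1.2 has the action taken with study drug recorded for each event. If the summary uses that field, the cases may be kept, but the safety table and the disposition table can then disagree.

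   Neither document says which source applies, and neither plans a combined count or a separate listing.

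3. **What is unaffected.** The event is still recorded (Protocol 7.1.2) and still enters the SAP 7.3 tables by system organ class, preferred term, severity and relationship. Vital signs (SAP 7.7), positive eC-SSRS findings (SAP 7.10) and concomitant medicines (SAP 7.11) are reported regardless of the termination reason.

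4. **Consequence of a prohibited medicine.** Protocol 7.1.7 treats discontinuation as required. Protocol 7.1.9 and 11.1.2 leave it to a decision on the individual patient. Appendix B asks patients who were not on a preventive at baseline not to start one, but states no consequence.

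5. **Illustrative size.**
   - Planned enrolment: 867 + 675 + 300 = 1842 (Protocol 9.1).
   - Anticipated dropouts: 0.30 × 1842 = 552.6, about 553.
   - Assumed share of dropouts coded under the exception: 0.5% to 5%. This range is not from the documents.
   - Patients moved: 0.005 × 553 = 2.8 to 0.05 × 553 = 27.7, so about 3 to 28.
   - As a share of enrolment: 2.8/1842 = 0.15% to 27.7/1842 = 1.5%, that is 0.15 to 1.5 percentage points.

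   The Appendix B list is written for patients not using preventives at baseline, so the exposed group is smaller than all 1842.

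**The case against.** The strongest defence is that the exception is narrow. It does not reach every adverse event that leads to a prohibited medicine, only those judged insufficient on their own to stop treatment. An event that itself warrants stopping stays coded as an adverse event. The event must also require a prohibited medicine, and Appendix B ends by allowing unlisted drugs of the same classes, and listed drugs given topically or as eye drops. The discretion in 7.1.9 and 11.1.2 narrows it further. All of this stands, and it points to a low frequency. It does not make the exception empty. For example, Protocol 1.4.1.1 names back pain among commonly reported events, and Appendix B disallows daily NSAIDs for other indications as a class, not as a list of named drugs.

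A reader might infer more than the documents support, in three ways.

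- **That the drug's key risks are hidden.** Protocol 1.4.1.1 lists as a potential risk "cardiovascular consequences of CGRP inhibition, including effects on blood pressure, heart rate, or other cardiovascular parameters", and Appendix B names beta-blockers, several antidepressants and "angiotensin receptor blocker: candesartan and lisinopril". It is tempting to conclude that blood-pressure, heart-rate and mood events are the ones most likely to be recoded. The same-class allowance undercuts that, and those events remain visible in the outputs under item 3 of the working. On mood, the eC-SSRS is a safety endpoint, but the PHQ is an exploratory efficacy measure.
- **That removal from the SAP 7.3 table is established.** It is an inference, because the source field is undefined. Only the change to the termination-page reason, and so to disposition, follows directly from the text.
- **That the understatement can be quantified.** If a share *s* of true adverse-event withdrawals is recoded, the reported rate is the true rate times (1 − *s*). The relative understatement is then simply the assumed share, and the documents give no basis for choosing it.

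It is also fair that withdrawal due to adverse events is a planned summary, not one of the safety endpoints listed in Protocol 9.7.1.

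**Conclusion.** The point holds in a limited form. Section 7.1.7 departs from its own default for one group of patients. The departure can only lower adverse events as a reason for withdrawal in disposition, and it may also lower the SAP 7.3 summary. No planned analysis recovers the cases. What is lost is the link between event and withdrawal, not the event.

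Confidence is high on the rule and its direction, and low on its size. The frequency is unknown and probably small. The 3 to 28 patients above rest entirely on an assumed share of the anticipated 30% dropout. Because the tolerability figure bears on the primary objective and the remedy is cheap, the change is worth making even if few patients are affected.

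Separately, 7.1.7 conflicts with 7.1.9 and 11.1.2 on whether a prohibited medicine must end participation. The passages need to be reconciled; this review does not say which is right.

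**What to change.** - Keep the termination-page reason as it is, but link the triggering adverse event to it on the CRF.
- State in SAP 7.3 which field identifies adverse events causing discontinuation.
- State in SAP 7.3 that the summary and listing include withdrawals coded as prohibited medication where the medicine was needed to treat an adverse event. Alternatively, show these on a separate line with a combined count.
- Reconcile Protocol 7.1.7 with 7.1.9 and 11.1.2. Deleting the exception outright is not proposed, because that would bear on the clinical rule itself.

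The cost is a few sentences and one CRF link. Much of the information is already collected: indication and start and stop dates for concomitant medicines (Protocol 5.3), and treatment given and action taken for each adverse event (Protocol 7.1.2). The downside is that the reported rate of withdrawals linked to adverse events may rise slightly.
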